7.10. VISIT WINDOW GUIDE

Visit Name	Calculate from:	Window Start Day	Window Stop Day
Pre-Implant / Implant Data	Enrollment date	- 90	0
Hospital Discharge (completed prior to actual discharge)	Implant date	0	30
ACT / DAPT Discontinuation or Planning Visit	Implant date 90 days after Implant date preferred	30	180
1 st CT-scan Follow-up Visit (no ACT/DAPT)	Hospital Discharge date 30 days after Hospital Discharge preferred	30	90
1 st CT-scan Follow-up Visit (DC on ACT/DAPT)	ACT / DAPT Discontinuation date	60	240
2 nd CT-scan (if needed) A minimum of 6 weeks after 1 st CT-scan	Implant date	180	300
1 year follow-up	Implant date	335	395

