6.3.6. STUDY ENDPOINTS DEFINITIONS AND ASSESSMENTS

The primary endpoint will be evaluated with statistical hypothesis tests formally defined in Section 10.

Primary endpoint

The primary endpoint is the incidence of reduced leaflet motion identified through 4D volume-rendered CT imaging at minimum 1 month after the end of the anticoagulation or dual antiplatelet therapy (expected within 1 to 6 months post-implant, preferably 3 months), as assessed by an independent Core Lab. Enrolled subjects not receiving anticoagulation or antiplatelet therapy at discharge will be assessed via 4D volume-rendered CT imaging at a minimum of 30 days after hospital discharge.

• Secondary endpoints

The secondary endpoints are as follows:

- 1. Incidence of reduced leaflet motion (thrombus) with subanalysis in symptomatic and asymptomatic subjects, based on CT outcomes, and anticoagulation and dual antiplatelet treatment modalities, up to 1 year post-implant.
- 2. Incidence of reduced leaflet motion on 2nd 4D volume-rendered CT scan with contrast up to 1 year post-implant, in subjects in which reduced leaflet motion was previously detected.
- 3. Incidence and relationship of reduced leaflet motion to the device, procedure, or other causes up to 1 year post-implant.
- 4. Freedom from valve safety events (all-cause mortality, valve reintervention, myocardial infarction, structural valve deterioration, moderate or severe valve regurgitation, valve endocarditis, valve thrombosis, thromboembolic events, hemolysis and major bleeding) up to 1 year postimplant.
- 5. NYHA classification at 1 year post-implant.
- 6. Hemodynamic performance up to 1 year post-implant through TTE assessed by Echocardiographic Core Lab.

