7.5. ANTICOAGULATION / DUAL ANTIPLATELET DISCONTINUATION (OR PLANNING) VISIT

This visit may be done by the subject's primary care physician as part of the standard of care for the subject. If done at a location other than the research location, the documentation of the visit will need to be obtained, reviewed by the site PI, and filed in the subject's research records. The visit details may then be entered in the EDC

system and made available for monitoring/source data review. Any part of the evaluation not completed will be considered a protocol deviation.

For subjects discharged with anticoagulation or dual antiplatelet therapy, (see Appendix 4 for American College of Cardiology guidelines for anticoagulation therapy¹¹) an additional visit shall be performed to assess the possibility to stop the anticoagulation or antiplatelet therapy and plan the CT scan. The discontinuation of anticoagulation or antiplatelet therapy is usually around 3 months after surgery in subjects without a further clinical need for this treatment. This additional visit shall evaluate the following information:

- Subject status
- Physical evaluation (including cardiac rhythm and NYHA functional classification)
- Medications
- SAEs

Subjects which are not able to come off ACT/DAPT treatment will remain in the study and followed through the 1-year evaluation.

7.6. 1ST CT SCAN VISIT (1 TO 6 MONTHS FOLLOW-UP VISIT)

This visit is intended to be done a minimum of 30-days after the initial discontinuation of anti-coagulation or dual antiplatelet therapy; usually between 1-6 months postimplant, or at least one month after discharge for subjects discharged without anti-coagulation therapy. Follow-up evaluations are to be conducted in an office, hospital or clinic setting and are to be performed by the PI or his/her designee.

The following data listed below shall be collected:

- Subject status
- Physical evaluation (including cardiac rhythm and NYHA functional classification)
- Medications
- Hemodynamic data from TTE examination measured at investigational site (MPG; PPG, EOA, aortic regurgitation with severity and location)
- CT Scan

- TEE only in subjects that are unable to undergo CT scan at the time of followup
- Medications
- SAEs

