8.1. TABLE 2 SCHEDULE OF STUDY PROCEDURES

Procedure	Pre- Implant / Implant Data	Hospital Discharge	ACT / DAPT Discontinuation (or Planning) Visit	1st CT-Scan Follow- up Visit	Reduced Leaflet Follow-Up (2 nd CT- Scan)	1 Year Follow- Up	Unscheduled Visits
Applicable Subjects	All Subjects	All Subjects	Subjects on ACT / DAPT	All Subjects	Subjects with Reduced Leaflet Motion on 1st CT Scan	All Subjects	Subjects with reduced leaflet function symptoms or other condition needing study related Follow-up
	After	≤ 30 days of Implant	1 – 6 mo.	Non-ACT/DAPT Pts. 30 days after Hospital Discharge (+ 60 day window)	6 - 10 mo	1 year after the	At Discretion
Timing	Successful Implant	(before the subject is discharged)	Post-Implant (3 mo. preferred)	ACT/DAPT Pts. 30 days after ACT/DAPT Therapy discontinuation (+ 60 day window)	Post-Implant	surgery (± 30 day window)	of Investigator
Informed Consent	×						
Inclusion / Exclusion (confirmed Post-Implant)	×						
Subject Characteristics	×						
Medical History (including previous cardiovascular procedures)	*						
Surgical Details	×						
Concomitant Procedures	×						
Physical Evaluation (Vitals / ECG± / NYHA Classification)	*X	×	×	×	X	X	ŦΧ
Post-operative ECG	×						
Transesophageal	×						
FF01346E	TRIAL CODE	TRIAL CODE: APRO02 CIP Version N° B	Version N° B	Page 33/61	1_		

FF01346E

TRIAL CODE: APRO02 CIP Version N° B

This document contains information which LivaNova PLC deems CONFIDENTIAL and PROPRIETARY; therefore it shall not to be used, duplicated, or disclosed in whole or in part without the prior written consent of LivaNova PLC.

(SOC)

BRIEVE $\overset{\mathbb{H}}{\times}$ \mathbf{x} * × × × * × × × * × × × × × × × × *** *** × Serious Adverse Events and CT scan 4 D (with contrast) Medications Assessment echocardiogram (TEE) echocardiogram (TTE) **Transthoracic** Outcomes

*A transesophageal echocardiogram (TEE) may be performed in subjects that are unable to undergo CT scans.

Collected from Pre-Implant Data. NYHA classification will be collected from pre-implant history. TTE should be done within 3 months of implant.
◆ May occur prior to implant if the PI & subject have already determined a LivaNova Perceval bioprosthetic valve will be implanted.

± If available as standard of care procedure

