5.4 DEFINITIONS

Investigational Device (ID)	PERCEVAL (PMA P150011)
Baseline	Last non-missing observation (scheduled or unscheduled) before implant.
	Measurements collected the day of implant, in absence of other time information, are considered baseline data.
	If a subject is missing the planned baseline collection, the previous non-missing evaluation will become the baseline value.
	If any observation will be available before or on the day of implant, an unscheduled assessment done before the discharged visit can be used as baseline.
Study Day Count	The day of implant is defined as study Day 1.
	Calculate the study day according to the following rules:
	If date < study Day 1 then study day = Date – study Day 1
	If date ≥ study Day 1 then study day = Date – study Day 1 +1

LN-GLB-CLN-TEM-0033 rev1 Page 10 of 42

Study phases	
Pre-implant (Screening)	Screening and pre-implant assessments, where informed consent is signed and eligible criteria are met, before subjects will be considered enrolled in the study.
Implant (Enrollment)	During the implant until the establishment of a successful procedure.
Hospital Discharge	Before the subject is discharged or within 30 days of implant.
ACT/DAPT discontinua- tion visit	Visit required only for subjects on ACT/DAPT at hospital discharge: from 1 to 6 months (3 months preferred) postimplant.
Follow-up evaluations: First CT scan	Minimum of 30 days (+ 60 days) after discharge or discontinuation of ACT/DAPT (expected from 1 to 6 months post-implant).
Second CT scan	For subject with reduced leaflet motion previously detected by Core Lab; after the 1^{st} CT scan, but prior to 1 year follow-up visit (expected from 6 to 10 months post-implant).
1 year	Clinic visit at 1 year ± 1 month after the day of the implant.
Pre-implant period	Period from signing of the informed consent until the day before the implant.
Post-implant period	Period from successful implantation of Perceval bioprosthetic heart valve to 30-days after hospital discharge visit (for subjects discharged off ACT/DAPT) or ACT/DAPT discontinuation visit (for subjects discharged on ACT/DAPT).
Post-ACT/DAPT period	Period from 31 st day after the hospital discharge (for subjects discharged off ACT/DAPT) or 1 st day after the ACT/DAPT discontinuation (for subjects discharged on ACT/DAPT) to 1 year visit.

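### For subjects discharged on ACT/DAPT, the Visit Window Guide puts the first CT at days 60-240 after discontinuation, while the schedule and the SAP text say 30 days (+60), i.e. days 30-90.

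*Protocol*

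**What the plan says.** **Visit Window Guide.** In Protocol 7.10, the row "1 st CT-scan Follow-up Visit (DC on ACT/DAPT" counts from the ACT/DAPT discontinuation date, with start day 60 and stop day 240. SAP Figure 2 prints the same row. The row above it, "1 st CT-scan Follow-up Visit (no ACT/DAPT", counts from hospital discharge and gives days 30 to 90.

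**Schedule and SAP text.** Protocol 8.1 sets the scan at "30 days after ACT/DAPT Therapy discontinuation (+ 60 day window", and SAP Figure 1 repeats this. SAP 5.4 has "Minimum of 30 days (+ 60 days) after discharge or discontinuation of ACT/DAPT", and the first-CT bullet in SAP 18.6 agrees with it.

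**Minimum time off therapy.** Protocol 7.6 asks for "a minimum of 30-days after the initial discontinuation of anti-coagulation or dual antiplatelet therapy". The primary endpoint in Protocol 6.3.6 is read "at minimum 1 month after the end of the anticoagulation or dual antiplatelet therapy". SAP 10.1 also uses 30 days.

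**Timing of the stop.** Protocol 7.5 says that discontinuation "is usually around 3 months after surgery in subjects without a further clinical need". The Guide gives the planning visit implant days 30-180, with day 90 preferred.

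**Which source governs.** SAP 18.6 says that measurements are assigned by the protocol windows shown in Figure 2. Its next sentence says that these windows are defined in SAP 5.4.

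**The concern.** Two windows with the same anchor give different days for the scan that decides the primary endpoint. A site that books by the schedule and aims for day 30 after discontinuation is early under the Guide. A site that books by the Guide can scan as late as day 240, which is 150 days after the schedule closes.

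Two things depend on which window is used. One is the time off therapy at which leaflet motion is observed in these subjects. The other is which scans are marked as out of window. SAP 9 counts visits marked in that way against compliance. SAP 6.4 removes subjects with major primary-endpoint-related deviations from the per-protocol set, and sensitivity analysis 2 uses that set.

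**Working it through.** **Inputs.** Guide: 60 and 240 from discontinuation (Protocol 7.10, SAP Figure 2). Schedule: 30 plus a 60-day window from discontinuation (Protocol 8.1, SAP 5.4, SAP 18.6). Planning visit: implant days 30-180 (Protocol 7.10). One month is 30.4375 days (SAP 18.7).

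**1. Reproducing the printed figures.**
- Off-therapy row: 30 to 30 + 60 = 90. The Guide prints 30-90, so it reproduces.
- On-therapy row, same rule from discontinuation: 30 to 90. The Guide prints 60-240, so it does not reproduce.
- Counted from implant instead: 30 + 30 = 60 and 180 + 60 = 240. This returns the printed numbers, but not from the printed anchor. It also gives the latest stop only 60 days in total, where 30 (+60) would end at 180 + 90 = 270.

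**2. Overlap, in days after discontinuation (inclusive).**
- Schedule: 90 - 30 + 1 = 61 days.
- Guide: 240 - 60 + 1 = 181 days.
- Both: 90 - 60 + 1 = 31 days.
- Either: 61 + 181 - 31 = 211 days.
- Schedule only: days 30-59, 30 of 61 days (49%), including the day-30 target.
- Guide only: days 91-240, 150 of 181 days (83%).

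**3. In implant days.** This assumes that therapy stops on the day shown, at the start, preferred day and end of the planning window. Six months is 6 × 30.4375 = 182.6, so day 182 is the last full day inside it.

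| Stop day | Schedule window | Schedule days within 6 months | Guide window | Guide days within 6 months |
|---|---|---|---|---|
| 30 | 60-120 | 61 of 61 | 90-270 | 93 of 181 |
| 90 | 120-180 | 61 of 61 | 150-330 | 33 of 181 |
| 180 | 210-270 | 0 of 61 | 240-420 | 0 of 181 |

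The schedule window itself passes 6 months for any stop after day 92 (182 - 90). Late scans are therefore not peculiar to the Guide. The Guide's closing day is later by 240 - 90 = 150 days at every stop.

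**4. If the row was meant to count from implant.** For a stop on day 90, 30 days off therapy is reached on day 120. Implant days 60-119 (60 days) would then be in window with too little time off therapy. For a stop on day 180, the schedule runs over days 210-270, and days 241-270 (30 days) would fall outside 60-240.

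**The case against.** The best defence is that the documents do point to 30 (+60). SAP 18.6 refers to SAP 5.4 for the definitions, and 5.4 carries that rule. Protocol 7.9 and 8 tie data collection to the schedule of procedures. The 60-240 pair looks like a range in implant days with the wrong anchor cell. This much stands: a careful programmer would probably settle on 30 (+60), so it would be too strong to say that the SAP offers no rule. But SAP 18.6 also names Figure 2 as the source and prints it with the conflicting row. The implant-day explanation is an inference, and it only moves the error to the anchor cell. Nor can the Guide be a loose outer limit, since it excludes half of the schedule window.

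A reader might infer more than the documents support:
- *That compliance for on-therapy subjects would reverse completely under the other window.* SAP 9 works from deviations marked in the e-CRF and reports by visit for the safety population, with no breakdown by therapy. The documents do not say which window is used for marking.
- *That this row alone causes scans beyond 6 months or too late for a timely second CT.* Late stops can produce both under the schedule as well. The 1-6 months is also stated as an expectation, not a limit.
- *That early or late scans drop out of the primary analysis.* SAP 10.3 uses the first CT result in the safety population, and no rule excludes an out-of-window scan.

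**Conclusion.** The conflict is real, and it is minor. The on-therapy row is wrong as printed in both documents: either its days or its anchor must change. The row reads the same in both, so damage in text extraction is unlikely.

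Its size can be given in days only. The windows agree on 31 of 211 days. For a stop on the preferred day 90, the schedule gives implant days 120-180 and the Guide gives 150-330. The number of subjects affected cannot be derived.

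The consequence is inconsistent scheduling of the first CT and inconsistent flagging of deviations. Whether a flagged scan also leaves the per-protocol set depends on the Risk Based Study Management Plan, which is not among the documents. No effect on the primary incidence estimate is claimed. The implant-day figures assume stop dates within the planning-visit window.

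**What to change.** In Protocol 7.10 and SAP Figure 2, change the on-therapy first-CT row to start day 30, stop day 90, counted from the ACT/DAPT discontinuation date. Protocol 7.10 and 8.1 and SAP 5.4 and 18.6 then give one rule.

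If 60-240 days from implant was intended, correct the anchor cell instead and state the 30-day minimum off therapy as a separate condition.

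The cost is one row in two tables, with no new visit, procedure or analysis. The downside is that first CTs already done on days 91-240 after discontinuation, in line with the Guide, become window deviations and should be listed as such.

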7.11. BLINDING OF CT IMAGING RESULTS

Blinding of CT imaging results, for the purpose of evaluation of reduced leaflet motion, has been implemented to minimize the PI's exposure to imaging information that would typically not be obtained through standard of care practices. This blinding is intended to

prevent influence of the subject's (medical) treatment based on the possible findings of the CT scan.

To limit access and visibility of the CT images they will be sent directly to the Core Lab, which will be responsible for the assessment. Core Lab findings will not be sent to the site or accessible to sites in the EDC system. If, through assessment of the CT scan, the Core Lab becomes aware of findings that would potentially jeopardize subject safety (i.e. thrombus), the PI will be notified. Any medical circumstance requiring the PI's access to the CT scan or imaging results will lead to unblinding of the PI, possible unblinding of the subject, and may result in an adjustment of the subject's treatment (including medication) based on the PIs discretion.

For asymptomatic subjects, PIs and subjects will be blinded from the CT imaging results and from the Core Lab findings. Investigators will be requested to not alter relevant antiplatelet or anticoagulation drug therapies for asymptomatic subjects. The need for and use of antiplatelet or anticoagulation drug therapy will be assessed at each follow-up visit.

Symptomatic subjects and the PI can be unblinded to CT imaging results based on any treatment deemed necessary by the PI or treating physician. In this case, the PI can request CT scan results from the Core Lab as they will not be automatically sent to the site. Symptomatic subjects are those with clinical symptoms, such as, but not limited to shortness of breath, fatigue, or signs of thromboembolic events, as assessed by the treating physician. Asymptomatic subjects with reduced leaflet mobility on their 1st CT scan, and who have an increase in valve gradients, may be unblinded. This determination will be made by the Core Lab and/or Coordinating Investigators, and revealed to the study site through the LivaNova Project Manager or designee.

For all subjects (symptomatic and asymptomatic), the PI will receive notification that a reduced leaflet follow-up including a 2nd CT scan is required to be scheduled within 6 to 10 months post implant. Unblinding may be performed after the second (2nd) CT Scan is completed if the findings from the Core Lab suggest continued reduced leaflet mobility, or any finding that may be determined to put the subject at risk. During the site initiation visit, sites will be trained and provided with instructions regarding the flow of CT scan data between the site imaging department, Core Lab, and the site to preserve the blind. These instructions will be maintained in the site study file. Subjects inadvertently unblinded will remain in the study and continue to be followed.

8. SCHEDULE OF STUDY PROCEDURES

Subject data will be collected on electronic Case Report Forms (eCRFs) provided by the Sponsor for all subjects giving informed consent. Subjects will be considered enrolled only after a successful implant of the Perceval aortic heart valve. Data, including SAEs, will be collected and recorded on eCRFs in the electronic data capture (EDC) system for the required study visits according to the following **Table 4: Schedule of Study Procedures**. After the data is entered onto the eCRFs, it will be checked for consistency and completeness. Inconsistent or incomplete data will be clarified by the study site through a query process.

8.1. TABLE 2 SCHEDULE OF STUDY PROCEDURES

Procedure	Pre- Implant / Implant Data	Hospital Discharge	ACT / DAPT Discontinuation (or Planning) Visit	1st CT-Scan Follow- up Visit	Reduced Leaflet Follow-Up (2 nd CT- Scan)	1 Year Follow- Up	Unscheduled Visits
Applicable Subjects	All Subjects	All Subjects	Subjects on ACT / DAPT	All Subjects	Subjects with Reduced Leaflet Motion on 1st CT Scan	All Subjects	Subjects with reduced leaflet function symptoms or other condition needing study related Follow-up
	After	≤ 30 days of Implant	1 – 6 mo.	Non-ACT/DAPT Pts. 30 days after Hospital Discharge (+ 60 day window)	6 - 10 mo	1 year after the	At Discretion
Timing	Successful Implant	(before the subject is discharged)	Post-Implant (3 mo. preferred)	ACT/DAPT Pts. 30 days after ACT/DAPT Therapy discontinuation (+ 60 day window)	Post-Implant	surgery (± 30 day window)	of Investigator
Informed Consent	×						
Inclusion / Exclusion (confirmed Post-Implant)	×						
Subject Characteristics	×						
Medical History (including previous cardiovascular procedures)	*						
Surgical Details	×						
Concomitant Procedures	×						
Physical Evaluation (Vitals / ECG± / NYHA Classification)	*X	×	×	×	X	X	ŦΧ
Post-operative ECG	×						
Transesophageal	×						
FF01346E	TRIAL CODE	TRIAL CODE: APRO02 CIP Version N° B	Version N° B	Page 33/61	1_		

FF01346E

TRIAL CODE: APRO02 CIP Version N° B

This document contains information which LivaNova PLC deems CONFIDENTIAL and PROPRIETARY; therefore it shall not to be used, duplicated, or disclosed in whole or in part without the prior written consent of LivaNova PLC.

(SOC)

BRIEVE $\overset{\mathbb{H}}{\times}$ \mathbf{x} * × × × * × × × * × × × × × × × × *** *** × Serious Adverse Events and CT scan 4 D (with contrast) Medications Assessment echocardiogram (TEE) echocardiogram (TTE) **Transthoracic** Outcomes

*A transesophageal echocardiogram (TEE) may be performed in subjects that are unable to undergo CT scans.

Collected from Pre-Implant Data. NYHA classification will be collected from pre-implant history. TTE should be done within 3 months of implant.
◆ May occur prior to implant if the PI & subject have already determined a LivaNova Perceval bioprosthetic valve will be implanted.

± If available as standard of care procedure

8.2. HANDLING OF STUDY DISCONTINUATIONS

8.2.1. Handling of Subject Temporary Treatment Discontinuation or Termination

For all subjects reaching the end of the study (completed 1 year visit, death, or explants) or in case of premature withdrawal as described in Section 6.3.5 (lost-to-follow-up, or subject's decision) a study termination form will be filled out in order to document the date and reason for discontinuation.

Every attempt must be made to have all subjects complete the follow-up visit schedule. A subject will be considered lost to follow-up when all efforts to obtain information are unsuccessful. At a minimum, the effort to obtain information must include at least two (2) attempts to make contact via phone, and a certified letter should be sent to the subject's last known address. Both phone contacts and copy of the letter must be documented/available in the subject's medical record and recorded in the eCRF. For subjects discontinued by the PI for a safety reason, the PI shall document the reasons for the decision.

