6.3.5. CRITERIA FOR SUBJECT TERMINATION

All enrolled subjects will be followed until the end of the study except upon premature discontinuation in the study. Participation of a subject in the study should be discontinued when:

- The exclusion from the study is required for the subject's safety,
- Relevant IRB and/or regulatory authority withdraw approval(s),
- The subject decides to withdraw from the study,
- The surgeon decides it is no longer in the subjects best medical interest to continue, or
- The subject is lost to follow up.

The subject may withdraw his/her consent or cooperation (i.e. the subject refuses to participate further in the study) at any time without jeopardizing the normal standard of care.

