13.2. Data Safety Monitoring Board (DSMB)

A Data Safety Monitoring Board (DSMB) will not be established for this study. As noted in Section 12.2 of the protocol Unanticipated Adverse Device Effects will be reported to the FDA and Institutional Review Board in accordance with FDA & IRB regulation. LivaNova will review the study data for subject safety throughout the life of the study and collect all serious adverse events once a subject is enrolled in the study until the end of their participation.

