5.2 DESCRIPTIVE STATISTICS

Descriptive statistics will be calculated using as reference the number of subjects in the relevant analysis population (any exception will be specified) according to the nature of the data as follows:

Study: APR002 BELIEVE

- Continuous variables: number of non-missing observations, arithmetic mean, standard deviation, minimum and maximum values, median and quartiles.
 - If there are less than 5 observations, only the number of non-missing observations, arithmetic mean, median, minimum and maximum will be presented.
- Categorical variables: number of non-missing observations (n), the number of missing and the relevant percentage on the analysis population, number and relative frequencies. If not defined otherwise, the percentage denominator will be the number of subjects with nonmissing information.
 - In case of subcategories, the relative frequencies will be calculated based on the subjects in the subcategory, in this case a footnote will be added explaining the different denominators.
- Time-to-event variables: number of non-missing observations (n), minimum, first quartile, median including 90% CI, third quartile, and maximum. For calculating the survival estimate 90% CI bounds the log-log transformed estimate of CI bounds will be used. Greenwood formula will be used to estimate the variance of the log-log transformation of the Kaplan-Maier estimator.

In addition, Kaplan-Meier estimates and plots will be provided with:

- o the respective number at risk and the Kaplan-Meier estimates at time points 1 month, 3 months, 6 months, 9 months and 1 year.
- o the median and its 90% Cl.
- o the Hazard Ratio (HR), its 90% CI and the relevant p-value, when applicable.

Subjects ongoing and who are free from event at the analysis cut-off date will be censored at the analysis cut-off date. Subjects who have discontinued without an event will be censored at the date of discontinuation.

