12.2.3 Valve re-intervention

Overview tables on valve re-intervention will be generated by overall using the SAF:

- 1) Summary of the number and percentage of subjects with at least one:
- valve re-intervention
- valve re-intervention with valve explants
- re-intervention without valve explants
- valve in valve procedure

The percentage denominator will be the number of subjects in the SAF.

2) For subject with at least one re-intervention with valve explants or valve in valve procedure, summary of the number and percentage of subjects:

Study: APR002 BELIEVE

- with at least one another valve implanted
- survived
- died

The percentage denominator will be the number of subjects with at least one re-intervention with valve explants or valve in valve procedure.

- 3) If >5% of subjects with more than one re-intervention, summary of the number and percentage of re-intervention for:
- valve re-intervention
- valve re-intervention with valve explants
- re-intervention without valve explants
- valve in valve procedure

The percentage denominator will be the total number re-interventions.

4) If >5% of subjects with more than one re-intervention with valve explants or valve in valve procedure, summary of the number and percentage of re-intervention with at least one another valve implanted. The percentage denominator will be the number of re-interventions with valve explants or valve in valve procedure.

All re-intervention details will be listed in subject listing sorted by and subject ID.

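### Protocol 8.2.1 makes explant an end-of-study event while other sections expect 1-year follow-up of every subject, so deaths after explant may go uncounted in 1-year mortality

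*Protocol*

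**What the plan says.** **Text under which explant ends participation**

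- Protocol 8.2.1 opens with "For all subjects reaching the end of the study (completed 1 year visit, death, or explants", set apart from premature withdrawal. For both groups, "a study termination form will be filled out in order to document the date and reason for discontinuation".
- Protocol 13.2 has the sponsor "collect all serious adverse events once a subject is enrolled in the study until the end of their participation".

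**Text under which everyone is followed to 1 year**

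- Protocol 6.3.5: "All enrolled subjects will be followed until the end of the study except upon premature discontinuation in the study". Explant is not among the discontinuation reasons listed there.
- Protocol 8.2.1, second paragraph: "Every attempt must be made to have all subjects complete the follow-up visit schedule". It makes no exception for explant.
- Protocol 4.2 expects participation from enrollment through the 1-year follow-up. The schedule in 8.1 assigns the 1-year visit to all subjects. Section 10.8 places the final analysis after all enrolled subjects have had that visit.

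**Analyses that use what happens after explant**

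- Protocol 6.3.6, secondary endpoint 4: "Freedom from valve safety events (all-cause mortality, valve reintervention, myocardial infarction" and further events, up to 1 year. SAP 11.5 analyses each as its own time-to-event outcome.
- SAP 12.2.3: "For subject with at least one re-intervention with valve explants or valve in valve procedure, summary of the number and percentage of subjects" with another valve implanted, survived, and died.
- SAP 5.2, repeated in 18.13: "Subjects who have discontinued without an event will be censored at the date of discontinuation".

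**The concern.** A site that follows the first sentence of 8.2.1 completes a termination form at explant and has no instruction to contact the subject again. A site that follows the second paragraph, or 4.2, keeps the subject to 1 year. Both can claim to comply, so follow-up after explant could differ between sites.

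Closure at explant puts two results at risk. The first is 1-year all-cause mortality: the subject would be censored at explant, and Kaplan-Meier assumes that censored subjects go on to have the same risk as those still followed. A subject whose valve has been removed may not. The second is the survived/died summary in SAP 12.2.3. It pools explanted subjects with valve-in-valve subjects, and only explant is on the end-of-study list. One row would therefore mix status at the termination form with status at 1 year.

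Follow-up that was not collected cannot be restored by analysis, so this should be settled while subjects are still being followed.

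**Working it through.** **1. Denominator.** Protocol 10.2 needs 75 evaluable scans and assumes 15% attrition: 75 / (1 − 0.15) = 88.2, which matches the stated figure of approximately 88. No figure in the plan is disputed. One death is 1/88 = 1.1 percentage points.

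**2. Can a death after explant reach the analysis if the site closes the subject?**

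- SAP 18.11 identifies deaths from a fatal SAE outcome, an SAE criterion of death, or a termination reason of death.
- If the subject was terminated for explant, the termination reason is not death.
- Under Protocol 13.2, SAE collection has stopped, so neither SAE route records a later death.
- A death at the redo operation, before the form is completed, can still be recorded.

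**3. Which censoring rule applies?** SAP 5.2 never mentions explant. It has two rules: ongoing event-free subjects are censored at the analysis cut-off, and discontinued subjects at discontinuation. A closed subject is not ongoing, and the form in 8.2.1 records a reason for discontinuation, so the second rule is the natural reading. For the outcome valve re-intervention, explant is itself the event. For death and other events not yet experienced, the subject would be censored.

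**4. Repeat re-interventions.** The tables in SAP 12.2.3 items 3 and 4 are produced only if more than 5% of subjects have more than one: 0.05 × 88 = 4.4, so at least 5 subjects. With the few explants considered below, these tables are unlikely to be triggered.

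**5. Possible size for mortality (illustration on assumed inputs).** The documents give no explant rate and no mortality after explant. Let *d* be deaths among subjects not explanted, *k* the explants (all taken as early, which maximises lost follow-up) and *q* mortality after explant.

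- Estimate with censoring at explant ≈ *d* / (88 − *k*)
- Full follow-up = (*d* + *kq*) / 88

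Example with *d* = 6, *k* = 2, *q* = 50%: 6/86 = 6.98% against 7/88 = 7.95%, a difference of 0.98 points.

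Understatement in percentage points for *d* = 6:

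| Explants | q = 10% | q = 25% | q = 50% |
|---|---|---|---|
| 1 | 0.04 | 0.21 | 0.49 |
| 2 | 0.07 | 0.41 | 0.98 |
| 3 | 0.10 | 0.61 | 1.46 |
| 4 | 0.13 | 0.81 | 1.95 |

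Over the same grid, *d* = 4 gives 0.06 to 2.06, and *d* = 9 gives −0.03 to 1.79. The difference is zero when *q* = *d* / (88 − *k*), for example 6/86 = 7.0%, that is, when explanted subjects die at the same rate as the others.

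The range for *d* is also an assumption. Protocol 2.3.1 reports pooled mortality of 3.4% early and 7.0% late. Adding them gives 88 × 0.104 = 9.2 deaths, but the late deaths are not stated to fall within 1 year, so 9 is a high value.

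**6. Against the precision available.** The exact 90% interval for 7/88 is 3.8% to 14.4%. The illustrated differences are small beside it.

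**The case against.** The strongest counter-argument is that nothing in the documents says follow-up stops at explant. Section 8.2.1 asks only for a form, and its own next paragraph, with 4.2, 6.3.5, 8.1 and 10.8, points to 1-year follow-up for all subjects. This largely stands. A reader might infer that events after explant are never collected by design; the documents do not support that. They support a conflict that sites could resolve either way. The 6.3.5 text helps less than it seems, since it runs to the end of the study, which 8.2.1 says explant reaches.

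A reader might also infer that 1-year survival is biased upward. That depends on closure at explant and on higher mortality afterwards, and neither is established.

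Nor is the SAP 12.2.3 table emptied. Valve-in-valve subjects remain in follow-up, another valve implanted and death at the redo operation can be recorded for explanted subjects, and the repeat re-intervention tables have their 5% trigger.

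It is also fair to object that thromboembolism or bleeding after explant may belong to a replacement valve, possibly of another model. Whether to count such events is an estimand choice, so a blanket rule against censoring them would go too far. All-cause mortality is different: it is an outcome of the subject and does not depend on which valve is in place.

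**Conclusion.** The point holds as an internal conflict with a possible effect on two secondary results. Protocol 8.2.1 and 13.2 allow a subject to be closed at explant, other sections expect 1-year follow-up, and the SAP does not say how explant is handled in each time-to-event outcome. If sites close subjects at explant, later deaths would be missing from 1-year all-cause mortality, and survived in SAP 12.2.3 would cover different periods for explanted and valve-in-valve subjects.

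The size is unknown. The illustration runs from about zero to about 2 percentage points, resting on an assumed 1 to 4 early explants, 4 to 9 other deaths, and 10% to 50% mortality after explant. The number affected is probably small. Protocol 10 describes the study as descriptive and non-confirmative, and the primary endpoint is touched only if explant comes before the first CT. Severity is minor to moderate; the material does not support treating it as a defect that undermines the study.

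**What to change.** 1. **Protocol 8.2.1:** remove explant from the end-of-study list. State that after explant, vital status, SAEs and further re-interventions are collected to a 1-year contact, with events after explant labelled as such. Align 13.2 so that SAE collection runs to the same point.
2. **SAP 5.2 and 18.13:** state that all-cause mortality is not censored at explant.
3. **SAP 11.5:** for each remaining outcome, prespecify whether explant censors, with the reason.
4. **SAP 12.2.3:** state the time to which survived refers, the same for explanted and valve-in-valve subjects.

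The cost is a short protocol amendment, a few sentences in the SAP and a 1-year status contact for what is probably a handful of subjects. The sample size does not change. The one added burden is marking events that occur on a replacement valve. If some subjects have already been closed at explant, report how many and the date to which their vital status is known.
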